1.1 Background and rationale

The majority of injuries in Norwegian youth occur in a sports setting (1). Sports injuries are a significant public burden in terms of healthcare costs and place the individual youth at higher risk of developing subsequent health problems (2, 3). Additionally, sports-active youth often reduce or altogether cease their engagement in sports and physical activities following injury (4). The down-stream consequences of injuries sustained during sports should therefore not be underestimated. Football and handball are the most popular sports among Norwegian youth. The combination of the high physical demands inherent to these sports and the ongoing process of growth and maturation makes youth football and handball players notably susceptible to injury (5-7). Common injuries observed among youth who play football and handball encompass muscular and ligamentous ruptures, bone stress injuries, and injuries to the growing physes (5, 8).

Several injury prevention programs are effective in reducing injury occurrences. Soligard, Myklebust (9) showed a reduction in injuries overall, overuse injuries, and severe injuries in youth female football by implementing the FIFA 11+ injury prevention program. This multicomponent program, which targets both neuromuscular control and muscle strength, was subsequently adapted for specific populations, such as FIFA 11+ Kids (10) and a tailored shoulder injury prevention program for goalkeepers (11). Other efficacious injury prevention programs targeting specific injuries include the Nordic Hamstring for hamstring muscle ruptures (12) and Copenhagen Adductor Exercise for adductor muscle ruptures (13). In handball, structured warm up programs have proven efficacious in preventing lower extremity injuries and shoulder injuries (14-16). However, the gap between efficacy trials and real-world implementation remains a significant challenge.

Against this backdrop, the #Utviklingsklar project commenced in 2021. It is a collaborative and knowledge-sharing project funded by the Research Council of Norway. The overall aim of the project is to develop and evaluate a new program, based on interdisciplinary program theory from sport sociology, biomedicine, and health behavior, to reduce first-time and recurrent injury in youth football and handball. The project follows the UK Medical Research Council (MRC) framework for developing complex health interventions (17). The MRC framework emphasizes the importance of research methods that focus not solely on efficacy, but also on the mechanistic workings of an intervention, and whether it can be implemented in a real-world setting (17).

During the first two years of the project, we undertook development and feasibility testing of the novel #Utviklingsklar intervention. *#Utviklingsklar* is a club-based intervention designed to improve injury-preventive coaching practices. By participating in the intervention, coaches and club leaders develop plans and practices for injury-preventive warm-ups, strength training, and management of players with current pain and injury. The program theory underpinning the intervention is based on previous research within this field, preliminary work conducted in the research project, public involvement, and established theoretical

STATISTICAL ANALYSIS PLAN for Effectiveness of the Injury-preventive Program #Utviklingsklar

frameworks. First, we conducted a comprehensive literature review to dissect the biomedical mechanisms underlying the effect of injury prevention programs in football and handball. This review culminated in the formulation of causal biomedical models informed by previous research. Second, a cross-sectional study on behavioral constructs using the Health Action Process Approach was conducted, garnering responses from 865 youth football and handball coaches and players. Outcomes revealed a distinct need for increased knowledge, self-efficacy, and tools to aid coaches in managing pain and injuries in youth players. Third, a second literature review was conducted, focusing on the influence of sociocultural forces on injuries in the youth sport context. Critical to the developmental process was extensive knowledge exchange with the sporting community through meetings and discussion with project partners NIF, NHF, NFF, and key end users (club leaders, coaches, youth players, and their parents). Results from the preliminary work and feedback from stakeholders guided intervention development and content. The feasibility assessment, conducted with participation of three clubs from youth football and handball, prompted minor program revisions and indicated that a large-scale evaluation was warranted.

The current statistical analysis plan describes the evaluation of #Utviklingsklar in football. The project is embedded within the context of Norwegian youth sport. Findings from this evaluation will guide future initiatives to protect youth health among project partners NIF, NHF and NFF. It is therefore of primary interest to investigate how injuries are affected by the #Utviklingsklar program compared to usual practice, which may or may not involve other initiatives to prevent injury.

Central to the evaluation is the hypothesis that injuries in the youth sporting context are influenced by injury-preventive coaching practices. These practices encompass injury-preventive warm-ups, injury-preventive strength training, and management of players with pain and injury, including adjusting training and match loads and guiding youth towards appropriate medical care when necessary. Moreover, these coaching practices are hypothesized to be influenced by specific behavioral determinants, alongside the broader sociocultural context and interpersonal dynamics inherent in the youth sport setting. The current evaluation aims not only to produce knowledge on how injuries are affected by the implemented intervention, but also how the intervention affects factors in the proposed causal pathway, as outlined in the program theory.

STATISTICAL ANALYSIS PLAN for Effectiveness of the Injury-preventive Program #Utviklingsklar

1.2 Trial Objectives

1.2.1 Primary Objective

The primary objective is to compare the effectiveness of #Utviklingsklar to usual practice on the weekly injury severity score in youth football players over one season.

1.2.2 Secondary Objectives

The secondary objectives are:

- To compare the effectiveness of #Utviklingsklar versus usual practice on injury consequences in youth football players over one season.
- To compare the effectiveness of #Utviklingsklar versus usual practice on football youth coaches' determinants of injury-preventive behavior at mid-season and end of season.
- To compare the effectiveness of #Utviklingsklar versus usual practice on injury-preventive coaching practice among youth football coaches over one season.

2. Trial Methods

2.1 Trial Design

The evaluation follows the MRC framework for complex interventions (17). The study is conducted by a parallel two-armed, pragmatic, superiority cluster-RCTs. Clubs are randomised to either the control group that continue their activity as normal or the intervention group participating in #Utviklingsklar. #Utviklingsklar includes a digital e-learning course, an in-person workshop, and a club meeting, all three activities involving participation of one club leader and a minimum of one coach from each participating team within each club.

2.2 Randomisation

Upon enrolment, clubs will be randomly assigned to either the control or intervention group in a 1:1 allocation ratio, using a computer-generated cluster randomisation schedule, taking differences in cluster size into account and stratified by geographical region. The biostatistician responsible for the randomisation and primary statistical analysis will be blinded to group allocation. It is impossible to blind players, coaches, and clubs to group allocation. For practical reasons (i.e., data monitoring and participant follow-up), neither the PhD students nor the principal investigator will be blinded.

2.3 Sample size

Sample size calculation has been based on the primary endpoint (using player weekly injury severity score during the study period of one season). Sample size estimations under varying assumptions for cluster size and effect were performed by the project biostatistician. Data from one previous study in the target population were used to estimate the average weekly injury severity score in the control group and expected standard deviation. Assuming club sizes of 64 players, 13 clubs in each trial arm are sufficient to detect a difference between the average weekly injury severity score of 34 (intervention group) and 25.5 (control group), with a pooled standard deviation of 30, 80% power, 2-tailed alpha of 0.05, and an ICC of

STATISTICAL ANALYSIS PLAN for Effectiveness of the Injury-preventive Program #Utviklingsklar

0.05 or less. This corresponds to a relative reduction of 25%. We will overshoot recruitment by four clubs to allow for potential withdrawal of clusters. The target number of clubs to recruit is therefore 15 in each trial arm. As cluster sizes are large, the risk of type II errors due to individual participant data loss is minor.

2.4 Statistical Framework

2.4.1 Hypothesis Test

The primary null hypothesis is that there is no difference between #Utviklingsklar and usual practice in the injury severity score in youth football players over one season. There is only one identified primary analysis. All other effectiveness analyses will be regarded as supportive.

2.4.2 Decision Rule

This trial is designed to address a single primary outcome. A group difference is claimed if the primary null hypothesis is rejected on the significance level (alpha) of 0.05 (two-sided).

2.5 Statistical Interim Analyses and Stopping Guidance

There will be no interim analysis in this trial. Due to the projects' assumed low risk of harm or unforeseen events for participants, along with a short project duration and data collection period, the establishment of an independent data monitoring committee is not deemed necessary. There is also no perceived necessity for routine collection and evaluation of adverse events.

2.6 Timing of Outcome Assessments

All planned measures and data collection are scheduled according to figure 1. Besides the baseline data collection, questionnaires are kept open for submission for two weeks (players) and three weeks (coaches) at each data collection timepoint. These periods are referred to as outcome assessment windows.

Activities	Participant	-1	0	T1	T2	T3
		Pre study Recruitment and consent	Pre study Baseline	Study Pre-season	Study In-season	Study Post-season
Recruitment and consent	Players, parents, coaches, club leaders	x				
Randomization	Club		x			
Quantitative data collection						
Demographics questionnaire	Players, coaches, club leaders		x			
Injury surveillance*	Players				x	
Behavior questionnaire	Coaches		x		x	x
Injury-preventive coaching practices	Coaches		x			x

*Conducted with biweekly measurements through the season

Figure 1. Timeline of outcome assessments of #Utviklingsklar.

- Pre-study baseline coaches: 11.02.2025.-31.03.2025
- Pre-study baseline players: 23.03.2025- 08.05.2025
- Study in season coaches: 23.09.2025-21.10.2025

STATISTICAL ANALYSIS PLAN for Effectiveness of the Injury-preventive Program #Utviklingsklar

- Study in season players: week 17, 19, 21, 23, 25, 27, 29, 31, 33, 35, 37, 39, 41 and 43 of 2025. Players piloted their questionnaire during the recruitment phase, these data are not included in the data collection time periods.
- Study post-season coaches: 06.11.2025-30.11.2025

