2.6 Timing of Outcome Assessments

All planned measures and data collection are scheduled according to figure 1. Besides the baseline data collection, questionnaires are kept open for submission for two weeks (players) and three weeks (coaches) at each data collection timepoint. These periods are referred to as outcome assessment windows.

Activities	Participant	-1	0	T1	T2	T3
		Pre study Recruitment and consent	Pre study Baseline	Study Pre-season	Study In-season	Study Post-season
Recruitment and consent	Players, parents, coaches, club leaders	x				
Randomization	Club		x			
Quantitative data collection						
Demographics questionnaire	Players, coaches, club leaders		x			
Injury surveillance*	Players				x	
Behavior questionnaire	Coaches		x		x	x
Injury-preventive coaching practices	Coaches		x			x

*Conducted with biweekly measurements through the season

Figure 1. Timeline of outcome assessments of #Utviklingsklar.

- Pre-study baseline coaches: 13.05.2024.-29.08.2024
- Pre-study baseline players: 26.08.2024- 17.11.2024
- Study in season coaches: 06.02.2025-02.03.2025
- Study in season players: week 42, 44, 46, 48, 50, 52 of 2024 and 2, 4, 6, 8, 10, 12, 14 of 2025. Players pilot tested their questionnaire during the recruitment phase, these data are not included in the data collection time periods.
- Study post-season coaches: 21.04.2025-07.05.2025

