5.1.1 General Definitions and Derived Variables

5.1.1.1 *Health problems*

A *health problem* is defined as any condition that reduces an athlete's normal state of full health, irrespective of its consequences on the athlete's sports participation or performance or whether the athlete sought medical attention. This constitutes an umbrella term that includes, but is not limited to, injury and illness. A health problem is further divided into injury and illness. *Injury* is defined as tissue damage or other derangement of normal physical function due to participation in sports, resulting from rapid or repetitive transfer of kinetic energy. *Illness* is defined as a complaint or disorder experienced by an athlete, not related to injury.

STATISTICAL ANALYSIS PLAN for Effectiveness of the Injury-preventive Program #Utviklingsklar

Illnesses include health-related problems in physical, mental or social well-being, or removal or loss of vital elements.

5.1.1.2 *Exposure*

Exposure is defined as the time during which athletes are at risk of injury and is recorded for each individual within a team. *Training exposure* is quantified as the weekly hours of training during the observation period. *Match exposure* is quantified as the weekly minutes of match play during the observation period.

5.1.1.3 *Match season*

The match season is defined as the week the most teams start their regular league season and the week where this season ends.

5.1.1.4 *The Oslo Sports Trauma Research Center Questionnaire on Health Problems*

The Oslo Sports Trauma Research Center Questionnaire on Health Problems (OSTRC-H2) is used to collect all player data. It consists of four key questions about health problems impact on 1) participation in sports, 2) training volume, 3) performance, and 4) symptoms of health problems during the past 7 days. It also contains additional questions on injury and exposure. The questionnaire is self-reported by players and is administrated biweekly throughout the match season.

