5.1.2 Primary Outcome Definition

The primary outcome is the weekly injury severity score during the match season. The injury severity score is derived from responses to each of the four OSTRC-H2 questions, measured at 14 time points during the match season (see Section 2.6). Each question is assigned a score ranging from 0 to 25, culminating in a total injury severity score from 0 to 100 at each time point. If a player reports more than one injury at a given data collection timepoint, the injury severity score will be calculated as the maximum of the reported injury severity scores.

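### Football SAP: the coach outcome called mid-season is collected in weeks 39–43 of a week 17–43 season, so it cannot answer the stated mid-season objective

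*SAP*

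**What the plan says.** All references are to the football part of the SAP unless handball is named.

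- Section 1.2.2 has as a secondary objective a comparison of the arms on coaches' "determinants of injury-preventive behavior at mid-season and end of season".
- Sections 5.1.3.2 and 5.1.4 define the outcome as change in each determinant score from baseline to mid-season and from baseline to end of season. Section 5.2.4 fits a mixed model to three time points with those labels.
- Section 2.6 gives the coach dates: "Pre-study baseline coaches: 11.02.2025.-31.03.2025", then "Study in season coaches: 23.09.2025-21.10.2025", then "Study post-season coaches: 06.11.2025-30.11.2025". Figure 1 labels the middle one in-season.
- The season is fixed indirectly. Section 5.1.1.3 states: "The match season is defined as the week the most teams start their regular league season and the week where this season ends". It gives no calendar dates. Section 5.1.2 says the primary outcome is "measured at 14 time points during the match season (see Section 2.6"), and section 2.6 lists them: "Study in season players: week 17, 19, 21, 23, 25, 27, 29, 31, 33, 35, 37, 39, 41 and 43 of 2025".

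The SAP does not define mid-season in any other way and does not explain the timing of the middle coach window.

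**The concern.** The objective, outcome definition, outcome table and model all refer to a mid-season score. The only data that can fill that role are collected at the end of the player surveillance period. A reader of the results would take the baseline-to-mid-season contrast as evidence on coach behaviour about halfway through the season, while most of the player follow-up was still to come. With the listed dates it is evidence on behaviour when the season is nearly over.

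This matters because section 1.1 states an aim of learning how the intervention affects factors on the proposed causal pathway. For that aim it matters when coach behaviour changed. A score from weeks 39–43 cannot show whether behaviour had already changed during the earlier player time points.

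**Working it through.** **Inputs (sections 2.6 and 5.1.2).** Player weeks 17, 19, …, 43 of 2025; coach windows 11 February–31 March (baseline), 23 September–21 October (in-season), 6–30 November (post-season).

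**1. Reproduce the SAP's count.** Odd weeks from 17 to 43: (43 − 17)/2 + 1 = 14 time points, as stated in 5.1.2.

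**2. Season span.** Using ISO weeks, Monday of week 17 is 21 April 2025 and Sunday of week 43 is 26 October 2025, a span of 188 days. The midpoint is 21 April + 94 days = 24 July (week 30).

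**3. Position of the window.** Position = days since 21 April ÷ span.
- Opens 23 September: 155/188 = 82.4%.
- Closes 21 October: 183/188 = 97.3%.
- Opening minus midpoint: 155 − 94 = 61 days.

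**4. Sensitivity to the season end.** The SAP gives no calendar dates for the season, so the end point is varied:

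| Season end assumed | Span (days) | Window opens | Window closes |
|---|---|---|---|
| Monday of week 43 (20 Oct) | 182 | 85.2% | 100.5% |
| Sunday of week 43 (26 Oct) | 188 | 82.4% | 97.3% |
| End of a two-week player window from week 43 (2 Nov) | 195 | 79.5% | 93.8% |
| Opening of post-season coach window (6 Nov) | 199 | 77.9% | 92.0% |

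**5. Check against the SAP's own halves.** The football sensitivity analyses in 5.2.1 split the season into time points 1–7 and 8–14. Time point 7 is week 29 and time point 8 is week 31, so halfway is about week 30, as in step 2. The coach window opens in week 39, which is time point (39 − 17)/2 + 1 = 12. Eleven of the 14 player weeks have ended by then.

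**6. Distance between the two follow-ups.**
- Minimum: 21 October to 6 November = 16 days.
- Maximum: 23 September to 30 November = 68 days.
- Window midpoints: 7 October to 18 November = 42 days.

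**7. Overlap of the two contrasts.** The baseline window midpoint is 7 March. To 7 October is 214 days; to 18 November is 256 days. The contrast labelled mid-season therefore covers 214/256 = 84% of the end-of-season interval. The range over possible response dates is 176/244 = 72% (baseline 31 March, follow-ups 23 September and 30 November) to 252/268 = 94% (baseline 11 February, follow-ups 21 October and 6 November). A score taken on 24 July would cover 139/256 = 54%.

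**The case against.** **The outcome is measured.** A reader might infer that the middle outcome is missing. It is not. A dated in-season score is collected before the last surveillance week ends, and it enters the model in 5.2.4. Section 2.6 calls it in-season, which is accurate, and prints the dates. This stands: the fault is that other sections call the same score mid-season.

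**The SAP claims no early or sustained effect.** Similar results at the two follow-ups could be misread as an early effect that lasted. The SAP plans two separate contrasts and says nothing about onset or maintenance, so there is no such claim to remove.

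**Sixteen days is the extreme.** It is the shortest possible gap between a coach's two responses. Window midpoints are 42 days apart, so the follow-ups are not duplicates. This also stands. The overlap in step 7 does not depend on the 16-day figure.

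**The timing may have a reason.** Section 3.2 names a mid-season meeting as an intervention component but gives no date. The window may have been tied to it, so the SAP alone does not show that the timing was badly chosen. Such a link would still leave label and calendar in disagreement.

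**Handball.** One might extend the point to the handball SAP, where the window "Study in season coaches: 06.02.2025-02.03.2025" lies at about 66–80% of that season. It closes 50 days before the handball post-season window opens, and no comparable consequence can be shown there.

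**Impact is limited.** Section 2.4.1 treats every analysis other than the primary as supportive. That is correct and bounds the importance of the point.

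**Conclusion.** The label and the dates disagree in the football SAP. The window for the mid-season coach score lies about 82–97% of the way through the season, and within 78–100% under every season end tried. No coach score is taken near mid-season, so the stated mid-season objective cannot be answered, and the two change contrasts share roughly 84% of their time span.

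This rests on reading the player surveillance weeks as the match season, which 5.1.2 supports; on ISO week numbering; and, for the 84% and 42-day figures, on responses near the middle of each window. The conclusion is confined to a supportive secondary outcome. The primary outcome, the player outcomes and the baseline-to-end-of-season coach contrast are unaffected. The documents do not show whether the label or the dates are the error.

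**What to change.** First, check the football coach dates in 2.6 against what was scheduled, and correct them if they are wrong. The listed in-season window runs 28 days from opening to closing, whereas the same section says coach questionnaires stay open for three weeks. That is one more reason to check, though not proof of an error, since the post-season window (24 days) also departs from three weeks.

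If the dates are right:
- In 1.2.2, 5.1.3.2, 5.1.4 and 5.2.4, replace mid-season with late in-season (weeks 39–43).
- Report the elapsed weeks since season start for this measurement.
- Interpret the contrast as a late-season effect.

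The cost is wording: no new data and no change to the model. What is lost is any football conclusion about coach behaviour at mid-season.

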2.7 Timing of Final Analysis

The main analysis is planned when all clubs have been given the opportunity to attend/conduct all parts of the intervention, data at the post-season assessments have been entered, verified and validated and the primary database has been locked.

3. Statistical Principles

3.1 Confidence Intervals and p-values

All calculated p-values will be two-sided and compared to a 5% significance level. If a p-value is less than 0.05, the corresponding group difference will be denoted as statistically significant. All effectiveness estimates will be presented with two-sided 95% confidence intervals. As there is only one primary hypothesis to be tested in this trial, there will be no adjustments for multiplicity.

